### **3.5. Simulation Results**

Operating characteristics are reviewed to investigate overall performance of the BLRM under each true scenario.

#### 4. HYPOTHETICAL DOSE ESCALATION SCENARIOS IN EARLY GROUPS

Aside from the overall operating characteristics studied above, the design should make reasonable decisions during a study based on the observed toxicities. After completion of a given group, the decision to dose escalate and actual dose chosen for the subsequent group will depend on the recommendation of the BLRM per EWOC principle and medical review of available clinical, PK/PD, and laboratory data.

CCI

CCI

A large, bold, red logo consisting of the letters 'CCI' in a stylized, rounded font. The letters are filled with a bright red color and have a thick, slightly shadowed outline. The logo is centered on a solid black rectangular background.

## 5. DISCUSSION

The Bayesian Logistic Regression Model for the dose-escalation enables us to incorporate the preclinical information, as well as to update the recommended dose based on all safety data in the study.

On-study recommendations based on the model are consistent with the clinical decision-making process and should be considered in conjunction with other available clinical information by the Nektar Clinical Trial Team and study Investigators in deciding the dose levels to be tested in order to determine the MTD/RP2D.

**APPENDIX 2: RESPONSE EVALUATION CRITERIA IN SOLID TUMORS (RECIST 1.1)**

Response Assessment	RECIST Guideline, Version 1.1
Target Lesions	
CR	Disappearance of all target lesions and reduction in the short axis measurement of all pathologic lymph nodes to $\leq 10$ mm
PR	$\geq 30\%$ decrease in the sum of the longest diameter of the target lesions compared with baseline
PD	$\geq 20\%$ increase of at least 5 mm in the sum of the longest diameter of the target lesions compared with the smallest sum of the longest diameter recorded OR The appearance of new lesions, including those detected by FDG-PET
SD	Neither PR nor PD
Non-target Lesions	
CR	Disappearance of all non-target lesions and normalization of tumor marker levels
SD	Persistence of 1 or more non-target lesions and/or the maintenance of tumor marker levels above normal limits
PD	The appearance of 1 or more new lesions or unequivocal progression If patient has measurable disease, an increase in the overall level or substantial worsening in non-target lesions, such that tumor burden has increased, even if there is SD or PR in target lesions If no measurable disease, an increase in the overall tumor burden comparable in magnitude with the increase that would be required to declare PD in measurable disease (eg, an increase in pleural effusions from trace to large, or an increase in lymphangitic disease from localized to widespread)

CR = complete response; FDG-PET = fluorodeoxyglucose (FDG)-positron emission tomography; PD = progressive disease; PR = partial response; SD = stable disease

Reproduced from [Eisenhauer, 2009](#).

CCJ

CCI

**APPENDIX 4: CLINICAL LABORATORY TESTS (ONLY TESTS DONE VIA CENTRAL LABORATORY)**

Clinical Laboratory Tests		
Hematology	Chemistry	Serology

 
• Hemoglobin (Hgb)
 
• Hematocrit (HCT)
 
• Red blood cell (RBC) count
 
• Platelet count
 
• White blood cell (WBC) count
 
• Neutrophils
 
• Lymphocytes
 
• Monocytes
 
• Eosinophils
 
• Basophils
 
• Mean corpuscular volume (MCV)
 
• Mean corpuscular hemoglobin (MCH)
 
• Mean corpuscular hemoglobin concentration (MCHC)
 
	
 
• AST (SGOT)
 
• ALT (SGPT)
 
• Alkaline phosphatase (ALP)
 
• Albumin
 
• Creatinine
 
• Calculated creatinine clearance
 
• Calcium
 
• Ferritin
 
• Gamma-glutamyl transferase (GGT)
 
• Glucose
 
• Total protein (TP)
 
• Total and direct bilirubin
 
• Sodium
 
• Potassium
 
• Chloride
 
• Magnesium
 
• Carbon dioxide (CO2) content or bicarbonate
 
• Blood urea nitrogen (BUN)
 
• Lactate dehydrogenase (LDH)
 
• Uric acid
 
	
 
• Hepatitis B surface antigen (HBsAg)
 
• Hepatitis B core antigens (anti-HBc)
 
• Hep B DNA
 
• Hepatitis C virus antibody (anti-HCV)
 
• Hepatitis C virus ribonucleic acid (HCV-RNA)
 
• Human immunodeficiency virus (HIV) antibody
 

Additional Labs		

 
• Creatine kinase (CK)
 
• Thyroid-stimulating hormone (TSH)
 
• Free thyroxine (free T4)
 
• Free or total triiodothyronine (T3)a
 
• Lipase
 
• Amylase
 
		
Coagulation		

 
• Partial thromboplastin time (PTT)
 
• Prothrombin time (PT)
 
• International normalized ratio (INR)
 
		
Urinalysis		

 
• Specific gravity
 
• pH
 
• Glucose
 
• Protein
 
• Bilirubin
 
• Ketones
 
• Leukocyte esterase
 
• Blood
 
	For positive protein, white blood cell or blood, a microscopic examination including: 
 
• Red blood cells
 
• White blood cells
 
• Epithelial cells
 
• Bacteria
 
• Crystals
 
• Casts
 
	
Minimal acceptable laboratory safety tests for local laboratory to assess suitability for retreatment of NKTR-255		
Hematology	Chemistry	

 
• Hemoglobin
 
• Platelet count
 
• Neutrophils including bands (absolute)
 
	
 
• Creatinine
 
• Sodium
 
• Potassium
 
• Chloride
 
• Calcium
 
• Bicarbonate/CO2
 
	

a. T3 should be tested in case of an abnormal TSH and normal T4. See the Laboratory Manual for further information.

**APPENDIX 5: ECOG PERFORMANCE SCALE**

ECOG Grade	ECOG Status
0	Fully active, able to carry on all pre-disease performance without restriction
1	Restricted in physically strenuous activity but ambulatory and able to carry out work of a light or sedentary nature, eg, light house work, office work
2	Ambulatory and capable of all selfcare but unable to carry out any work activities. Up and about more than 50% of waking hours
3	Capable of only limited selfcare, confined to bed or chair more than 50% of waking hours
4	Completely disabled. Cannot carry on any selfcare. Totally confined to bed or chair
5	Dead

ECOG = Eastern Cooperative Oncology Group

Source: [Oken, 1982](#).

**APPENDIX 6: CHRONIC KIDNEY DISEASE EPIDEMIOLOGY  
COLLABORATION (CKD-EPI) CREATININE EQUATION**

$eGFR = 141 \times \min(S_{Cr}/\kappa, 1)^\alpha \times \max(S_{Cr}/\kappa, 1)^{-1.209} \times$   
 $0.993^{\text{Age}} \times$   
1.018 [if female]  $\times$   
1.159 [if Black]

where:

$eGFR$  (estimated glomerular filtration rate) = mL/min/1.73 m^2

$S_{Cr}$  (standardized serum creatinine) = mg/dL

$\kappa$  = 0.7 (females) or 0.9 (males)

$\alpha$  = -0.329 (females) or -0.411 (males)

min = indicates the minimum of  $S_{Cr}/\kappa$  or 1

max = indicates the maximum of  $S_{Cr}/\kappa$  or 1

age = years

Source: [Levey, 2009](#).

**APPENDIX 7: ACCEPTABLE METHODS OF CONTRACEPTION**

Highly Effective Methods of Contraception	Progestogen-only hormonal contraception associated with inhibition of ovulation
	Hormonal methods of contraception including oral contraceptive pills (combination of estrogen and progesterone), vaginal ring, injectables, implants, transdermal and intrauterine hormone-releasing system (IUS)
	Bilateral tubal ligation
	Vasectomized partner
	Intrauterine devices (IUD)
	Complete abstinence
	Local laws and regulations may require use of alternative and/or additional contraception methods
Additional Method for Male Patients	Condom
	NOTE: Partners of male patients are to use one highly effective method of contraception
Unacceptable Methods for Contraception	Vaginal sponge with spermicide
	Progestin only pills
	Cervical cap with spermicide
	Diaphragm with spermicide
	Periodic abstinence (calendar, symptothermal, post-ovulation methods)
	Withdrawal (coitus interruptus)
	Spermicide only
	Lactation amenorrhea method (LAM)
	Male condoms with or without spermicide for partners of female patients, as the only method of contraception
	Female condoms
	A male and a female condom used together

## LIST OF ABBREVIATIONS

Abbreviation or Term	Definition
CCI	[REDACTED]
AE	Adverse Event
CCI	[REDACTED]
AST	Aspartate Aminotransferase
AUC	Area Under the Curve
BLRM	Bayesian logistic regression model
BMI	Body Mass Index
BOR	Best Overall Response Rate
C1D1	Cycle 1 Day 1
CC	Cervical Cancer
CBR	Clinical Benefit Rate
CI	Confidence Interval
CL/calCrCL	Calculated Creatinine Clearance
CM	Concomitant Medication
C max	Maximum Peak Concentration
CnDn	Cycle n Day n (e.g., Cycle 1 Day 1 = C1D1)
CR	Complete Response
CRC	Colorectal Carcinoma or Colorectal Cancer
CRF	Case Report Form
CRO	Contract Research Organization
CRS	Cytokine Release Syndrome
CCI	[REDACTED]
CT	Computed Tomography
CTC	Common Toxicity Criteria
CTCAE	Common Terminology Criteria for Adverse Events
DLT	Dose-Limiting Toxicity
DOR	Duration of Response
DSMC	Data Safety Monitoring Committee
EC50	Half Maximal Effective Concentration (EC 50 )
ECG	Electrocardiogram
ECOG	Eastern Cooperative Oncology Group
eCRF	Electronic Case Report Form
EGFR	Epidermal Growth Factor Receptor
EWOC	Escalation With Overdose Control
FDA	Food and Drug Administration
FIH	First in Human
HNSCC	Head and Neck Squamous Cell Carcinoma
HPV	Human Papillomavirus
hr	Hour
IRT	Interactive Response Technology

Abbreviation or Term	Definition
mAb	Monoclonal Antibody
MTD	Maximum Tolerated Dose
NA	Not Applicable
NCI	National Cancer Institute
ORR	Objective Response Rate
OS	Overall Survival
PD	Pharmacodynamic(s)
PD1	Programmed Cell Death Protein 1
PD-L1	Programmed Death Ligand 1
PEG	Polyethylene Glycol
PFS	Progression-Free Survival
PK	Pharmacokinetics
PR	Partial Response
PT	Prothrombin Time
PTT	Partial Thromboplastin Time
q21d	Every 21 Days
q28d	Every 28 Days
QTcB	Corrected QT interval using Bazett formula
QTcF	Corrected QT interval using Fridericia formula
RECIST	Response Evaluation Criteria in Solid Tumors
RP2D	Recommended Phase 2 Dose
R/R	Relapsed or Refractory
SAE	Serious Adverse Event
SAP	Statistical Analysis Plan
SFU	Survival Follow-up
sIL-15R $\alpha$	Soluble IL-15 Receptor Alpha
SOP	Standard Operating Procedure
SRC	Safety Review Committee
TEAE	Treatment Emergent Adverse Event
TP	Total Protein
TTR	Time to Response
TRTSDT	Treatment Start Date
ULN	Upper Limit of Normal
WBC	White Blood Cell

## 1.0 ADMINISTRATIVE STRUCTURE

This study will be managed via partnership between Nektar Therapeutics and a contract research organization (CRO). Central clinical laboratories will be used for processing of safety specimens, CCI [REDACTED] pharmacokinetic (PK), CCI [REDACTED] samples. An interactive response technology (IRT) service provider will manage the patient enrolment, study drug(s) distribution and inventory management. Data for this trial will be entered into an Electronic Data Capture (EDC) system, using a Medidata Rave platform. An independent data monitoring committee (DMC) is established to review the safety data on a periodic basis. Response and progression will be determined using Response Evaluation Criteria in Solid Tumors version 1.1 (RECIST 1.1).

## 2.0 INTRODUCTION

This document outlines the statistical methods to be implemented during the analyses of data collected within the scope of Nektar Therapeutics Protocol 19-255-03 “A Phase 1b/2, open-label, multi-center, dose escalation and dose expansion study of NKTR-255 monotherapy or in combination with cetuximab as a salvage regimen for solid tumors”, protocol amendment 2.0 dated 08 October 2021. The purpose of this plan is to describe the statistical analyses according to Section 9.0 of the study protocol along with any additional analyses, specifications or deviations from the protocol planned. Because only Phase 1b patients were enrolled for the study, this plan will focus on Phase 1b part. Any deviations from these guidelines will be documented in the clinical study report (CSR). All analyses will be conducted by Nektar Statistical Programming & Analysis (SPA) using SAS® Version 9.4 or later.

### 3.0 STUDY OBJECTIVES

This section shows planned primary, secondary, CCI from the study protocol. CCI

#### 3.1 Primary Objectives

Phase 1b (Dose Escalation):

To evaluate the safety, tolerability, as well as define the MTD and/or RP2D, of NKTR-255 in combination with cetuximab in relapsed or refractory (R/R) head and neck squamous cell carcinoma (HNSCC) CCI.

CCI

- [REDACTED]
- [REDACTED]

#### 3.2 Secondary Objectives

- To evaluate the efficacy of NKTR-255 monotherapy in R/R cSCC, ASCC, and cervical cancer by assessing the ORR by RECIST 1.1
- To evaluate the efficacy of NKTR-255 in combination with cetuximab and NKTR-255 monotherapy by assessing progression-free survival (PFS) and overall survival (OS)

CCI

## 4.0 STUDY ENDPOINTS

This section shows planned primary, secondary, and exploratory endpoints which are related to Phase 1b only.

### 4.1 Primary Endpoints

- Incidence of dose limiting toxicity (DLT), treatment emergent adverse events (AEs) in Phase 1b

### 4.2 Secondary Endpoints

- ORR by investigator assessment (per RECIST 1.1) in R/R cSCC, ASCC, and cervical cancer
- PFS and OS in NKTR-255 monotherapy and in combination with cetuximab

[figure not shown]

CCI

## 5.0 OVERALL STUDY DESIGN AND PLAN

This study is a Phase 1b/2, Open-label, Multicenter, Dose Escalation and Dose Expansion Study of NKTR-255 in patients with R/R HNSCC, CRC, CCI [REDACTED]. This section shows the planned study design including CCI Phase 1b CCI [REDACTED] in the protocol. Because no Phase 2 patients were enrolled in the study, this plan will focus only on analyses for the Phase 1b part.

**Figure 1:** Study Schema

CCI [REDACTED]

CCI [REDACTED]

Phase 2 dose

Note: No intra-patient dose escalation will be conducted in any cohort.

Note: The dose-limiting toxicity (DLT) window for NKTR-255 in combination with cetuximab is 21 days following the initial dose of NKTR-255.

CRC = colorectal cancer CCI [REDACTED]

HNSCC = head and neck squamous cell carcinoma; Ph = Phase; RP2D = recommended

## Phase 1b – Dose Escalation

The NKTR-255 starting dose will be 1.5 µg/kg, which had no safety concerns as defined by pre-specified dose limiting toxicities in the first cohort of the first-in-human (FIH) study Protocol 18-255-02. The starting dose is based on the safety data generated from the escalation cohorts and the RP2D determination from the FIH study. The starting dose will not be greater than the highest dose determined by the Safety Review Committee (SRC) to have no safety concerns in the FIH study.

After an initial cetuximab loading dose, patients will receive IV NKTR-255 every 21 days (q21d) in combination with cetuximab weekly. Beginning with Dose Level 1, successive cohorts of at least 3 patients each will receive ascending doses of NKTR-255 until the MTD and/or RP2D is determined. Approximately 30 patients may be enrolled in the dose escalation phase of the study. A 2-parameter Bayesian logistic regression model (BLRM) employing the escalation with overdose control (EWOC) principle (Neuenschwander, 2008) will be used as a guide during the escalation phase of the study for dose level selection and for determination of the MTD and/or RP2D. Additional dose levels may also be opened to further explore the MTD and/or RP2D.

The first patient (a sentinel patient) of each escalating NKTR-255 dose level will be monitored for safety and tolerability for 7 days after the first dose of NKTR-255 before additional patients are dosed within the same dose level. A composite of clinical information will be used to select the RP2D based on safety and tolerability, PK, CCI and optimal biological response. Additional patients may be enrolled to refine the RP2D, and a minimum of 6 patients will be required to define the RP2D

The dose limiting toxicity (DLT) window is 21 days after the first dose of NKTR-255. Patients who achieve optimal response (partial response [PR] or complete response [CR] as determined by RECIST 1.1) after at least 1 tumor assessment, as determined by the Investigator and in consultation with the Medical Monitor, will be given the option to continue treatment with NKTR-255 as single agent for maintenance every 28 days (q28d) at the same dose as the patient's originally assigned dose.

CCI

- Intermediate doses may be evaluated.
- No intra-patient dose escalation will be allowed.
- Enrollment into a new dose level with an escalating dose of NKTR-255 cannot begin until the DLT window has closed for the last patient in the prior dose cohort. The DLT window is 21 days after the first dose of NKTR-255.
- The SRC will assess safety before opening dose escalation to the next level.
- The Sponsor's decision to declare the RP2D of NKTR-255 can occur at any given dose level prior to reaching the MTD based on safety, PK CCI .
- Data from a minimum of 6 evaluable patients are required to define the RP2D.
- Dose reduction of NKTR-255 is not allowed during dose escalation within the DLT window. Outside of the DLT window in the dose escalation phase, and during dose expansion, dose levels of NKTR-255 may be reduced depending on the severity, duration, and frequency of toxicities observed at the previous dose level tested (the dose level may be de-escalated in order to characterize RP2D for a specific cohort).
- The cetuximab dose may be reduced or adjusted based on review of available safety and tolerability data. Dose adjustment or discontinuation for cetuximab may be required based on emerging toxicities and should follow the guidelines specified in the protocol and in the current Prescribing Information for Erbitux® (cetuximab).

CCI

## 6.0 STATISTICAL CONSIDERATIONS

### 6.1 General Considerations

The statistical analyses will be reported using summary tables, data listings and graphics as appropriate.

Unless otherwise specified, data collected during the dose escalation phase will be presented by dose level groups and overall. Continuous variables will be summarized with means, standard deviations, medians, minimums, and maximums. The means will be presented to one decimal place beyond which the data were captured. The standard deviation will be presented to two decimal places beyond which the data were captured. The minimum and maximum will be presented to the precision with which the data were captured.

Categorical variables will be summarized by counts and by percentage of subjects in corresponding categories. A row or column denoted 'Missing' will be included in count tabulations where necessary to account for dropouts and missing values. Percentages will be rounded to 1 decimal place and the percent will be suppressed when the count is zero. The denominator will be the number of subjects in the cohort of interest unless otherwise noted.

Unless specified otherwise, all 95% confidence interval for proportions will be two-sided and be based on the exact (Clopper-Pearson) method and confidence interval for the quartiles of time to event variables will be based on the Brookmeyer and Crowley method using log-log transformation (1982).

For analyses by visit, only data of scheduled visits will be reported, and nominal visits will be used. For analyses up to a certain time point, data of both scheduled visits and unscheduled visits up to that time point will be considered. For analyses of worst post-baseline value, both scheduled and unscheduled measurements will be included.

For BOR and PFS, both scheduled and unscheduled assessments will be included. The actual investigator response assessment dates will be used.

[figure not shown]
### 6.2 Determination of Sample size

#### 6.2.1 Sample Size Determination in Phase 1b

This is a Phase 1b/2 dose escalation and dose expansion study. During dose escalation (Phase 1b), successive cohorts of at least 3 patients will be treated at each dose level until the MTD and/or RP2D is determined. A 2-parameter adaptive Bayesian Logistic Regression Model (BLRM) with overdose control (EWOC) similar to that proposed by Babb et al. (1998) will be used to guide dose escalation in this study. After the completion of the DLT observation period of the last patient enrolled in a dose escalation level, the BLM will be re-run to obtain updated posterior probabilities of under-dosing, targeted toxicity, and excessive toxicity (see [Appendix 1](#) of Protocol Amendment 2.0) for all doses.

The dose recommended by the adaptive Bayesian logistic model will be regarded as guidance and information to be integrated with a clinical assessment of the toxicity profiles observed at the time of the analysis in determining the next dose level to be investigated. Generally, the study will not treat patients at a dose higher than the model-recommended dose. However, the study may escalate to or stay at a dose higher than the model-recommended dose if such a decision is consistent with accepted clinical practice (eg, standard 3+3 escalation rules serving as guidance). The dose given to the next dose level in the study will be based on considerations of the MTDs estimated by the BLRM. The overall clinical assessment of all available safety and tolerability, PK, and PD data may also be taken into consideration for the determination of dose given to the next dose level.

Additional patients may be added to each cohort based on the scheme and rules outlined in protocol Section [5.2.3.4](#) or Sponsor determination of the need for additional data to further evaluate the benefit/risk profile. **CCI**

The logo consists of the letters 'CCI' in a large, bold, red font. The letters are slightly slanted to the right. The background is black, making the red letters stand out.

### 6.3 Analysis Populations

**Enrolled Population:** All patients who receive at least 1 dose (or partial dose) of cetuximab or NKTR-255.

**Safety Population:** All patients who receive at least 1 dose (or partial dose) of NKTR-255.

**Cetuximab-only Population:** All patients who receive at least 1 dose (or partial dose) of cetuximab but without any dose of NKTR-255.

**DLT Population:** All patients who receive at least 1 dose of the combination treatment of NKTR-255 and cetuximab and who complete the DLT observation period or discontinue from

the study treatment due to a DLT will be included, where DLT window is 21 days since the first dose of NKTR-255.

**Response-evaluable Population:** The Response-evaluable Population is defined as patients who have measurable disease (per RECIST 1.1) at baseline, receive at least 1 dose (or partial dose) of NKTR-255, and have at least 1 post-baseline assessment of tumor response.

**Pharmacokinetic Population:** All patients in the Safety Population who receive at least 1 dose of treatment and have at least one evaluable PK concentration.

CCI

CCI

#### 6.4 Handling of Missing Data

**Every effort will be made to avoid missing/partial on-study data.**

Missing baseline data will not be imputed. This includes variables which are not allowed to be collected according to local regulations (e.g. race in France).

For post-baseline data, observations with values ‘not done’, ‘not evaluable’, ‘not applicable’ will be treated as missing values. For descriptive analyses, missing values will not be imputed. Number and percentage of missing values will be described separately. For analyses involve modeling, handling of missing values will be explicitly specified.

Detailed approaches for the imputation of missing information in death dates, AE start and end dates, cancer history diagnosis dates, and prior and concomitant medications start, and end dates are described below. Missing dates for surgery or procedures will use the same rules as for concomitant medications.

The general approach to handle partial dates are as follows:

- Dates with missing year information will not be imputed.
- Dates with missing month or day information will be imputed. Conservative imputation approaches will be adopted when applicable. For example, imputation rules for AE start and end dates are designed such that AEs with partially missing start dates will be included as TEAE if available information is not sufficient to decide whether AE starts before C1D1.
- Last known alive date, C1D1, the end of study follow-up date, informed consent date, etc. are used as reference dates to guide the imputation when applicable.

- 1) For the subsequent anti-cancer therapy start date:
  - If only the day is missing then: if the end date of the subsequent anti-cancer therapy is complete, impute to the minimum of (the last day of the month, end date of subsequent anti-cancer therapy); otherwise impute to the last day of the month.
  - If the month or year is missing, then leave missing.
- 2) For time from diagnosis of disease to treatment start date (TRTSDT), partial dates for initial diagnosis and diagnosis of disease will be imputed as follows:

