## 6.6 Definitions

### Run-in period:

Eligible patients on combination therapy will receive cetuximab 400mg/m^2 IV as a loading dose during the study run-in period (Day -7). The run-in period therefore starts from the time the patient receives cetuximab and ends when the patient receives combination treatment of NKTR-255 +cetuximab.

**Study drug or study treatment:** Study drug or study treatment refers to NKTR-255 or cetuximab.

**Study day:** Study Day 1 (C1D1) is the first day that the combination treatment of NKTR-255 +cetuximab begins.

**Baseline:** Unless otherwise specified, the baseline value for each variable is the last non-missing value collected at the time (if collected) closest to, but prior to, the start of NKTR-255 administration. For triplicate ECG data, the record with three non-missing value will be considered as non-missing. If multiple measurements occur on the same day at the same time, or on the same day but the time is not available, the average of the measurements (for continuous data) will be considered the baseline value. When dosing times and/or observation times are not collected, it is assumed that protocol planned in-office assessments obtained on the day of the first dose of study drug are prior to administration of the first dose of study drug and therefore considered baseline values.

**Last known alive date:** The date of last known alive date will be derived for patients unknown to have died or known alive at the analysis cut-off by using following dates:

- Patient assessment dates (blood draws **CCI** [REDACTED], vital signs, performance status, ECG, tumor assessments, ECOG, or tumor biopsy dates)
- Start and end dates of anti-cancer therapies administered after study treatment discontinuation
- AE start or end date
- Concomitant medication start or end dates
- Last date of contact collected on the 'Survival follow-up' eCRF (do not use date of survival follow-up assessment unless status is 'alive')
- Study treatment start or end date
- Date of discontinuation for study participation on disposition eCRF pages (do not use if reason for discontinuation is lost to follow-up)

Only dates associated with actual examinations of the patient will be used in the derivation. Dates associated with a technical operation unrelated to patient status such as the date a blood sample was processed will not be used.

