**Table 3: PFS Censoring Rules**

Situation	Date of Disease Progression or Censoring	Outcome
No post-baseline tumor assessments and no death	first dose date of Cetuximab	Censored
No progression and no death, and no new anti-cancer therapy started	Date of last assessment showing no evidence of disease progression	Censored
New anti-cancer therapy started without progression before	Date of last assessment before the start of anti-cancer therapy showing no evidence of disease progression	Censored
Disease progression reported on one or multiple response assessments without new anti-cancer therapy before	Date of earliest evidence of PD	Progressed
Death without PD or new anti-cancer therapy before	Date of death	Death
Two or more consecutive missing tumor assessments, and no progression before the missing assessment	Date of the last assessment prior to the missing assessment showing no evidence of disease progression	Censored

**Overall Survival (OS):** OS is defined as the time from the first dose date of Cetuximab to death from any cause. Patients will be followed until their date of death, loss to follow-up, or withdrawal of consent for further follow-up for survival, regardless of the start of anti-cancer therapy. Patients who are lost to follow-up will be censored at their last date known to be alive. Patients who do not have date of death at data cut-off date will be censored at their last date known to be alive. Patients who do not have any follow-up since first dose date of Cetuximab will be censored on the first dose date of Cetuximab.

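### SAP 6.4 can date a new anti-cancer therapy after the patient's death or after the contact that reported it, and leaves it undated when the month is unknown

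*SAP*

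**What the plan says.** SAP 6.4 (Handling of Missing Data), item 1, covers the start of subsequent anti-cancer therapy. If only the day is missing and the therapy's end date is complete, the start is set to the earlier of month-end and the "end date of subsequent anti-cancer therapy); otherwise impute to the last day of the month". For a start without month or year it says "If the month or year is missing, then leave missing".

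The general bullets above item 1 differ in two ways. One says "Dates with missing month or day information will be imputed". The next lists dates that may help where they apply: "Last known alive date, C1D1, the end of study follow-up date, informed consent date, etc. are used as reference dates to guide the imputation when" […]. Item 1 uses none of them.

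The start date is used in several places:

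- **PFS and DOR (SAP 6.6.1, Table 3).** New therapy without earlier progression censors at the last progression-free assessment before it. A death is an event only under "Death without PD or new anti-cancer therapy before". DOR follows the same censoring rules.
- **BOR (SAP 6.6.1 and 7.5).** Assessments after new therapy are excluded.
- **TEAE periods (SAP 6.6.1).** The 30-day NKTR-255 period and the 60-day extended period both end early at a new regimen. SAP 7.6.3 tabulates deaths within each period.

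**The concern.** A therapy cannot start after the patient has died, or after the date on which someone reported that it had started. Item 1 allows both. Because it picks the latest day in the month, any death later in that month is ordered before the therapy. Table 3 then counts a PFS death that the plan means to censor, and SAP 7.6.3 may count it as a death in the treatment-emergent period.

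When the month is unknown, the therapy is known to have been given but has no date. The SAP does not say whether Table 3, BOR and the TEAE periods then treat it as started, and a programmer has to guess.

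Partial dates are plausible here. Under Protocol 5.2.7, survival follow-up is a contact about every 3 months, by clinic visit, telephone, family or public records. TEAE incidence is a Phase 1b primary endpoint; PFS is secondary.

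**Working it through.** The plan gives no figure for this point, so there is none to reproduce. The checks below apply item 1 literally.

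**1. Size of the shift (day missing, no complete end date, true start day assumed uniform).** In a month of L days, the gaps from start day to month-end sum to L(L−1)/2. Over a 365-day year:

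(7 × 465 + 4 × 435 + 378) / 365 = 5,373 / 365 = **14.7 days** on average; median 15; maximum 31 − 1 = **30 days**.

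**2. Order of therapy and event in a 30-day month.** There are 30 × 29 / 2 = 435 day pairs with therapy first and 435 with the event first. Table 3's before is read as strictly before, except in the third row.

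| Rule | Therapy first, misordered | Event first, misordered |
|---|---|---|
| Month-end (item 1) | 435 of 435 | 0 of 435 |
| Month-end, capped at the event (death) | 435 of 435 | 0 of 435 |
| Same cap, a tie counts as therapy first | 0 of 435 | 435 of 435 |
| First of month | 0 of 435 | 406 of 435 |

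- A cap at death without a tie rule changes no PFS classification.
- For a death, the right-hand column is empty in reality, because therapy cannot start after death. The tie rule is therefore harmless if it is confined to deaths.
- For progression, the right-hand column is real. A first-of-month rule would place therapy before 406 of 435 events that truly came first.
- With a cap at the reporting contact (any day from start to event, equally weighted), 435 of 4,930 combinations (8.8%) stay misordered. In all of them contact and event share a day, and for deaths the tie rule settles these too.

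**3. Worked example.** Last scan, stable disease, 20 May; last NKTR-255 dose 25 May; call on 12 June reporting chemotherapy started in June; death 20 June; no therapy end date.

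- Item 1 gives 30 June: 30 − 12 = 18 days after the report and 30 − 20 = 10 days after death.
- Table 3 gives a PFS death on 20 June instead of censoring on 20 May.
- The NKTR-255 period runs to 25 May + 30 days = 24 June, so the death also falls inside it.
- With a cap at death only, therapy and death tie on 20 June, and under a strict reading the death is still an event.
- With a cap at the contact, therapy is dated 12 June, PFS is censored on 20 May, and the death falls outside the NKTR-255 period.

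**4. Extra days in the TEAE periods.** If the true start is g days after last dose (assumed range) and the period is W days, the gain is min(g + shift, W) − min(g, W). Averages over the shifts in step 1:

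| g (days) | 7 | 14 | 21 | 28 | 42 |
|---|---|---|---|---|---|
| W = 30 | 13.9 | 11.5 | 7.5 | 1.9 | 0 |
| W = 60 | 14.7 | 14.7 | 14.7 | 14.7 | 12.4 |

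**5. Scans.** With assessments every 9 weeks, 14.7 / 63 = 23% of such gaps would contain a scheduled scan, if scans continued.

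**6. Patients (assumed, not in the documents).** If 60% of about 30 patients start later therapy, that is 18. If 5–20% of those records are partial, that is 18 × 0.05 = 0.9 to 18 × 0.20 = 3.6. In an assumed 15-patient tumor-type table, one patient is 1 / 15 = 6.7 percentage points.

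**The case against.** **The reference-date bullet already prevents impossible dates.** It is relevant, but it names no operation and item 1 does not invoke it. Where the SAP wants such a bound it writes one: the death-date rule compares the imputed date with the latest unimputed alive date.

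**The missing-month rule is a specific exception to a general one.** That is a fair reading of the drafting. It still leaves open how a known but undated therapy is handled. A reader might infer that such a therapy is treated as never started; that is a likely programming result, but the SAP does not state it.

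**Little post-therapy data is collected.** This largely stands. Protocol 7.2 ends AE reporting, and Protocol 8.2 ends scheduled scans, at new anti-cancer therapy. What remains is deaths, unscheduled assessments (which the SAP uses) and data recorded before the site learned of the therapy. A spurious response is unlikely, because SAP 7.5 requires confirmation at least 4 weeks later.

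**The regimen is not flattered.** A reader might infer that the rule favors NKTR-255 plus cetuximab. In general it does not: extra PFS deaths and extra TEAEs count against the regimen. Only a response seen after new therapy would favor it.

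**OS is not clearly affected.** A reader might infer that survivors are censored after anyone knew them to be alive, since the last-known-alive sources in SAP 6.6 include "Start and end dates of anti-cancer therapies administered after study treatment discontinuation". But that definition ends by limiting the derivation to dates of actual examinations, which an imputed month-end is not. The two statements need one clarifying line; they do not establish an OS bias.

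**Conclusion.** The point holds as a defect in a stated rule. Item 1 can produce a start date after death or after the report of the therapy. With no complete therapy end date, every death later in the same month as the true start becomes a PFS event that Table 3 is meant to censor. The missing-month instruction conflicts with the general bullet, and the handling of known but undated therapy is unspecified.

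The effect is small. With only the day missing, the shift is at most 30 days and averages 14.7 under a uniform start day. The 0.9 to 3.6 patients rest on assumed rates and count all partial records. A PFS error in a day-missing record also needs no earlier progression, an event later in the same month, and no complete therapy end date before that event. PFS is secondary and summarized descriptively. The change is still worth making, because the rule yields impossible dates and is cheap to correct.

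A tempting stronger conclusion is that month-end is the wrong default and the earliest possible day should replace it. The enumeration does not support this: month-end keeps progression ahead of later therapy in all 435 pairs, whereas first-of-month loses 406.

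**What to change.** Revise SAP 6.4, item 1:

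1. Keep month-end as the default when only the day is missing. Cap it at the earliest of therapy end date, date of death, the contact at which the therapy was first recorded, and data cut-off.
2. State that a therapy whose imputed start ties with death counts as started before it. Confine this tie rule to deaths.
3. When the month is missing but therapy is known to have started, impute within the known bounds (after the last study dose, no later than the reporting contact) and align this with the general bullet. State how Table 3, DOR, BOR and the TEAE periods treat any therapy that stays undated.
4. In SAP 6.6, state that imputed therapy dates are not used for the last-known-alive date, in line with the sentence on actual examinations.
5. Use the earliest possible start (the later of the first of the month and the day after last study dose) only as a sensitivity analysis for PFS, DOR and BOR. As the primary rule it would censor true progressions that preceded therapy.

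Cost: a few lines of text, slightly more derivation code, and an occasional PFS death that becomes censored.
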